## **Mindfulness-based cognitive therapy for pain in cancer patients after primary treatment: An open implementation trial**

### **Background**

International research shows that untreated or undertreated pain among cancer patients after completion of therapy is a common problem with substantial negative impact on the patients' quality of life and mental and physical function [1-4]. A summary of literary reviews estimates that 19-41% experience pain between six months and five years after ended treatment [5]. While there are still relatively few Danish studies, this appears also to be the case in Denmark. Thus, in a national cohort of 3,343 women treated for breast cancer, we found that, respectively, 33% and 20% of the women reported pain "almost every day" or more 15 months and 7-9 years after treatment [6]. Based on a pain audit conducted at the Oncology Department at Aarhus University Hospital (AUH), we found that 50% had experienced pain in the past week, and that half of these patients had experienced pain for a month or more [7]. Among patients in follow-up care, 38% had experienced pain in the past week. A subsequent audit, at the Oncology Department, showed this percentage to be roughly unchanged (35%) [8], despite greater focus on education and patient interviews about pain. Research suggests that the extent of the problem may be due to 1) failure to identify patients with pain, 2) lack of or ineffective pharmacological pain therapy, and 3) adverse reactions to pharmacological pain therapy [9]. The first problem may be attributable to a lack of systematic screening for pain in oncology [10]. Our audit data shows that approx. 20% of patients had not spoken to hospital staff and that 60% had not spoken with their general practitioner about their pain [7, 8]. The second problem relates to the issue that even when patients with pain are identified and receive pharmacological pain therapy, many continue to experience pain [11, 12]. This is due, in part, to complex pain etiology, where cancer patients and cancer survivors' pain may be due to both the effects of the actual cancer and to the negative sequelae of the different cancer treatment's modalities, including surgery, chemotherapy, hormonal therapy and antibody therapy [3, 13]. Additionally, many cancer patients experience neuropathic pain [14, 15], which is difficult to treat pharmacologically, as confirmed by our data [7]. Finally, pharmacological therapy can result in adverse reactions, including memory and concentration difficulties, constipation, symptoms of depression, impaired reproductive function and sexual dysfunction [16]. These challenges have increased interest in psychological pain therapy. The benefits of psychological pain therapy include: 1) that psychological treatments are presumed to have little or no adverse effects; 2) that pain is a multidimensional phenomenon that involves complex connections between biological, psychological and social processes [17]; and 3) that newer meta-analytical studies document that psychological interventions are effective on both chronic pain in general [18], such as cancer-related pain, including among patients with mixed cancer forms [19] and, as we have demonstrated most recently, breast cancer patients [20]. Among the available methods of psychological intervention, mindfulness-based interventions (MBI) are of particular interest. MBI appears to be particularly relevant for pain, as mindfulness focuses, through different meditation exercises, on concentrating attention on here-and-now experiences and supporting new ways of addressing physical sensations and emotional discomfort, characterized by greater acceptance and openness [21]. MBI has been shown effective in treatment of nonmalignant chronic pain [22-24].

### **Objectives**

Aarhus University Hospital has adopted the reduction of late effects of cancer treatment as one of its core strategies [25]. As supported by the results of the pain audits at the Oncology Department at AUH completed

in 2011 [7] and 2014 [8], as well as in the nationwide cohort study of Danish women treated for breast cancer [6], persistent pain is a significant problem for many former cancer patients and survivors. We previously presented documentation on the effect on cancer-related pain of psychological interventions in general [20] and of mindfulness-based cognitive therapy (MBCT) in specific [26]. We therefore wish to extend the results of the previously published explanatory trial of MBCT for pain in cancer survivors [26] by conducting an open pragmatic trial focusing on the real-life implementation of MBCT in an oncology department and the generalizability in the everyday clinical setting of the results previously found for breast cancer survivors to all cancer patients who have completed their primary treatment and experience clinically significant pain. Specifically, the objectives of the present study are: 1) to executing the practical implementation in an oncology department of MBCT for patients who have completed their primary treatment and experience significant cancer- and cancer-treatment-related pain, 2) to evaluate effects on pain and well-being, 3) to explore patient satisfaction with the intervention offered, and 4) to explore possible organizational and individual physical, mental and socio-economic barriers for implementation in relation to drop-outs.

## **Methods**

### *Participants*

Inclusion criteria: Adult ( $\geq 18$  years old) cancer patients who have completed primary cancer treatment (excluding long-term anti-hormone therapy, e.g., tamoxifen) at the Oncology Department at Aarhus University Hospital and who are experiencing moderate to severe pain measured as a score of  $\geq 4$  (0-10 NRS) on the following pain dimensions: a) pain intensity, b) pain burden, c) pain impact (function) and/or d) perceived need for help with pain management. Exclusion criteria:  $< 18$  years of age, not yet completed chemo or radiation therapy, metastases, and serious psychiatric diagnosis, e.g., psychosis. Patients seen by all four diagnosis teams at the Oncology Department at AUH are screened for pain (0-10 NRS) in connection with their final consultation with the oncologist. Patients with a pain score of  $\geq 4$  on one or more of the four pain dimensions questions receive a folder describing MBCT and the treatment plan and are encouraged to contact the MBCT team for more information and scheduling of an interview. If the patient, after initial information either by phone or after the first interview decline the offer to participate, but are willing to be contacted for the purpose of gathering more information about their reasons for not participating, we will send them a brief questionnaire concerning their pain and their reasons for choosing to decline the offer, to complete online. They are also asked to give their permission to collect the same information after three months. All data are collected and registered with REDCap [27], a high data security project administration system administered by Aarhus University's Clinical Trial Unit. Based on the 2014 pain audit results, we anticipate that of approx. 3,250 annually completed treatment plans across diagnoses, about 400 cancer patients will experience clinically significant pain (NRS score of  $\geq 4$  on one out of four pain dimensions) after completed primary treatment. From our experience with psychological treatment of cancer patients, we conservatively anticipate that approx. 35% will accept the offer and that 15% will drop out early, resulting in approx. 120 patients per year. It should be noted that the true extent of the need for psychological intervention for pain in the department is yet unknown. The present implementation project will help to determine this.

### *Intervention*

As patients with significant pain are identified and accept the offer of receiving MBCT for pain, they will be consecutively included in groups of 12-20 participants. The patients will participate in eight weekly two hour

group sessions and will be asked to do an additional 45 minutes of daily training at home. The participants will be asked to record their home training to allow assessment of their adherence to the intervention. The program corresponds to the manualized MBCT program [28], but with adaptations that take into account the special needs of cancer patients [29, 30], including somewhat shorter sessions, shorter yoga exercises, and the omission of the all-day session. The sessions include psychoeducation and formalized mindfulness exercises with focus on the participants' here-and-now experience of their pain. According to the existing guidelines from Oxford Mindfulness Centre (OMC), Oxford University, where MBCT was developed, the instructor's professional and regular training, as well as supervision in MBCT, are critical for the quality of MBCT as intervention [31]. The instructors' training and supervision adhere to the OMC guidelines.

### *Evaluation*

The aim of the present project is to evaluate the *practical implementation* of MBCT, with focus on: 1) the observed effects on pain (*primary outcome parameter*), 2) effects on quality-of-life (QoL) and on other cancer and cancer-treatment-related late effects associated with pain (*secondary outcome parameter*), 3) possible barriers for continued participation in the program (drop-out), 4) patient experience and satisfaction with the intervention and its organizational/practical implementation, 5) staff's experience of screening procedure and implementation, and 6) collection of data for use in the evaluation of effects, costs, and savings. For use in the evaluation, the patients complete questionnaires prior to the first session (T1), immediately after the last session (T2), and at a six-month follow-up (T3).

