### *Instruments*

The patient-reported measures at T1, T2, and T3 include:

- 1) T1-T3: Pain measures (pain intensity, pain burden, pain impact (function), and the need for help with pain management) (0-10 pt. NRS). The primary effect measure is pain intensity, which has been shown a valid measure of pain in cancer patients [32].
- 2) T1-T3: The patients' pain profile is assessed using a list of pain descriptors from the McGill Pain Questionnaire [33] and the *Douleur Neuropathique en 4 Questions* [Neuropathic Pain in Four Questions] [34]. The descriptors cover somatic, visceral, neuropathic and affective pain [35].
- 3) T1-T3: General QoL is measured using the EQ5D [36]. Other secondary outcomes include: depressive symptoms (Beck's Depression Index [37]), sleep difficulties (the Insomnia Severity Index [38]), cancer-related QoL (EORTC-QLQ-C30 [39, 40]), fear of cancer recurrence (FCRI-SF [41]), dispositional mindfulness (the Five Facet Mindfulness Questionnaire [42]), and self-compassion (the Self-Compassion Scales [43]).
- 4) T2-T3: Patient-experienced satisfaction with the treatment plan (5-pt. Likert Scale) and open questions concerning any experienced difficulties and challenges in connection with participation in the treatment plan.
- 5) For use in planned assessments of costs and savings, the participants are asked for their permission to collect relevant data from national and local registries. On the end of the project period, we will also explore the staff's impressions of the screening procedures and implementation with a brief questionnaire. Non-participants who have agreed to be contacted for further information will be contacted by email or phone and answer: 1) the four pain dimensions (at time points corresponding to T1-T3) and 2) a questionnaire with closed and open questions concerning their reasons for not participating, e.g., time, geography, attitude

towards psychological pain intervention (barriers) and what help, if any, they receive to manage their pain, e.g., pain medication, physiotherapy, psychological help, own activities (resources) (T1).

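### Barriers to continuing are a stated objective, but the reasons questionnaire, the barriers analysis and the report item are written for patients who decline, not for those who stop

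*Combined protocol and SAP*

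**What the plan says.** Objective 4 (Objectives) is "to explore possible organizational and individual physical, mental and socio-economic barriers for implementation in relation to drop-outs". The third focus under Evaluation is "possible barriers for continued participation in the program (drop-out)".

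The collection of reasons is described in two places. Under Participants, patients who turn the offer down and agree to be contacted are the recipients: "we will send them a brief questionnaire concerning their pain and their reasons for choosing to decline the offer". A repeat is foreseen: "They are also asked to give their permission to collect the same information after three months". Under Instruments, non-participants receive "a questionnaire with closed and open questions concerning their reasons for not participating", and the reasons part is placed at T1. Item 4 of Statistical analysis studies nonparticipants' pain and their reasons. Item 3 of the first Dissemination list covers nonparticipation.

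Other material could reach patients who stop. Instruments item 4 (T2 and T3) includes open questions on "any experienced difficulties and challenges in connection with participation in the treatment plan". Evaluation also covers patients' satisfaction with how the programme was organised, and staff views of implementation. Intervention asks participants to log home training. All participants complete T1 before the first session.

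On numbers, Participants expects that "approx. 35% will accept the offer and that 15% will drop out early, resulting in approx. 120 patients per year". Under Intervention, "they will be consecutively included in groups of 12-20 participants".

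**The concern.** The protocol treats declining and dropping out as successive events: a patient first accepts, and some who accept later leave. The objective is about the second event, while the dedicated instrument, analysis and report item are about the first. Followed as written, the study would have direct data on why patients do not start and only indirect data on why they stop.

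The two sets of reasons may differ. The examples given for decliners are time, geography and attitude to psychological treatment. A patient who leaves may also be reacting to the sessions themselves, to 45 minutes of daily practice at home, or to how the groups are run. An implementation study needs to know this, and reasons not asked for when a patient leaves cannot be recovered reliably later.

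**Working it through.** **Expected numbers.** The inputs, all from Participants, are about 400 patients a year with clinically significant pain, 35% acceptance and 15% early drop-out.

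- Accepters: 400 x 0.35 = 140.
- Early drop-outs: 140 x 0.15 = 21.
- Remaining: 140 - 21 = 119, which reproduces the plan's approximate 120.
- Check of the base for the 15%: taken off all 400 instead, 400 x (0.35 - 0.15) = 80, which does not match. The 15% therefore applies to accepters.
- Decliners, the group the reasons questionnaire addresses: 400 - 140 = 260.
- Per group of 12 to 20 (Intervention): 12 x 0.15 = 1.8 and 20 x 0.15 = 3.0, so about 2 to 3 patients.

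**What 21 does and does not measure.** It is a planning assumption about early loss. If it includes accepters who withdraw before session 1, fewer than 21 of these patients stop after starting. It leaves out later drop-out, which would raise the total. The documents do not settle either point, because drop-out is not defined.

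**Objective against execution.**

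| Step | Patients who decline | Patients who start and stop |
|---|---|---|
| Named aim | Not among the four objectives or six evaluation focuses | Objective 4; Evaluation focus 3 |
| Reasons instrument | Questionnaire (Participants, Instruments) | None dedicated |
| Analysis | Statistical analysis, item 4 | None listed |
| Report item | Dissemination, item 3 | None dedicated |

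**What the indirect sources can supply.**

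- *T2 and T3 open questions.* They could elicit reasons, but only from those who still return a form. T2 follows the last session, so in a programme of eight weekly sessions a patient who leaves after session 1 would be asked about 7 weeks later. No analysis of the answers is listed.
- *Satisfaction and staff data.* Both bear on organisational barriers, but neither is linked to individual patients' stopping.
- *Home-training records.* They show adherence to the home practice, not the reason for leaving.
- *T1 measures.* They could describe physical and mental differences between those who stop and those who continue. The analysis section uses background variables only as possible moderators of pain change. T1 precedes any session, so it cannot show organisational barriers met during the programme.

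**How far the data could go.** As an illustration only, suppose 21 patients answered and 10 gave the same reason. The proportion is 10/21 = 48%, with a Wilson 95% interval of 28% to 68%. That supports description, not testing of predictors.

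**The case against.** The strongest reply is that the plan is not silent on patients who stop. The open questions on difficulties and challenges would naturally take in reasons for stopping, satisfaction with the organisation of the programme is an evaluation focus of its own, staff are surveyed, and home training is logged. The objective is exploratory and last of four, and no efficacy conclusion depends on it. A new form would also suffer from non-response.

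Much of this stands. A reader might infer that the plan collects nothing from drop-outs; the documents do not support that, given the sources just listed. Nor can one say that the open questions fail to ask why a patient stopped. The protocol only summarises them, so the supportable statement is that it does not say they ask this.

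What remains is that none of these sources is directed at patients who stop, and no analysis or report item draws them together to answer objective 4. One might also read nonparticipants broadly enough to include drop-outs. However, Participants ties the questionnaire to turning the offer down, by phone or after the first interview, and Instruments places the reasons at T1, before the first session. If the broader meaning is intended, the protocol should say so.

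**Conclusion.** The mismatch is real and should be corrected: a stated objective has indirect data sources but no dedicated instrument, analysis or report item. The scale is about 21 early drop-outs a year, or 2 to 3 per group, if the plan's 35% and 15% hold and the 15% applies to accepters. The number who stop after session 1 is uncertain in both directions.

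Two stronger readings are not supported. One is that the primary result is compromised. The analysis is by intention to treat, and how reasons for stopping are collected does not change it. The other is that 21 is a firm count of patients who will start and then leave. The text gives it only as an allowance for early loss and does not say when that loss occurs.

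**What to change.** 1. **Evaluation.** For objective 4 only, define drop-out as attending at least session 1 and stopping before session 8. Record accepters who withdraw before session 1 as a separate category and offer them the existing reasons questionnaire. State that the intention-to-treat set is unchanged and still includes all accepters with T1 data.
2. **Instruments.** When a patient stops, offer a voluntary adaptation of the reasons form, worded for not continuing, with added options for session content, home training and organisation.
3. **Statistical analysis.** Add a descriptive analysis of the number and timing of drop-outs, their stated reasons (together with the T2 and T3 open answers), and their T1 characteristics set against those who continue. Do not test predictors.
4. **Dissemination.** Report drop-out separately from nonparticipation.

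The cost is protocol wording and one short form in the existing REDCap system for a small number of patients. Response will be incomplete, the contact must not read as pressure to return, and the results will support description only.

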### *Instruments*

The patient-reported measures at T1, T2, and T3 include:

- 1) T1-T3: Pain measures (pain intensity, pain burden, pain impact (function), and the need for help with pain management) (0-10 pt. NRS). The primary effect measure is pain intensity, which has been shown a valid measure of pain in cancer patients [32].
- 2) T1-T3: The patients' pain profile is assessed using a list of pain descriptors from the McGill Pain Questionnaire [33] and the *Douleur Neuropathique en 4 Questions* [Neuropathic Pain in Four Questions] [34]. The descriptors cover somatic, visceral, neuropathic and affective pain [35].
- 3) T1-T3: General QoL is measured using the EQ5D [36]. Other secondary outcomes include: depressive symptoms (Beck's Depression Index [37]), sleep difficulties (the Insomnia Severity Index [38]), cancer-related QoL (EORTC-QLQ-C30 [39, 40]), fear of cancer recurrence (FCRI-SF [41]), dispositional mindfulness (the Five Facet Mindfulness Questionnaire [42]), and self-compassion (the Self-Compassion Scales [43]).
- 4) T2-T3: Patient-experienced satisfaction with the treatment plan (5-pt. Likert Scale) and open questions concerning any experienced difficulties and challenges in connection with participation in the treatment plan.
- 5) For use in planned assessments of costs and savings, the participants are asked for their permission to collect relevant data from national and local registries. On the end of the project period, we will also explore the staff's impressions of the screening procedures and implementation with a brief questionnaire. Non-participants who have agreed to be contacted for further information will be contacted by email or phone and answer: 1) the four pain dimensions (at time points corresponding to T1-T3) and 2) a questionnaire with closed and open questions concerning their reasons for not participating, e.g., time, geography, attitude

towards psychological pain intervention (barriers) and what help, if any, they receive to manage their pain, e.g., pain medication, physiotherapy, psychological help, own activities (resources) (T1).

### *Statistical analysis*

Intention-to-treat (ITT) analyses will be conducted with Multilevel Linear Models (MLMs). In the analysis, we will focus on 1) changes over time (T1-T3) in pain measurements. We will also compare patients who experience statistically (Reliable Change Index) [44] and clinically significant changes (NRS  $\geq 2$ ) [45] with the remaining patients. In the secondary analyses, we will focus on 1) effects on QoL and other secondary outcomes and explore the possible moderating influence of demographic and clinical background variables to changes in pain. Additionally, we will investigate 3) the staff's impressions of screening procedures and implementation. Furthermore, 4) nonparticipants will be studied with regard to changes in pain and reasons for not participating (barriers and resources). 5) If the implementation is deemed successful, cost analyses will be conducted on the basis of outcomes and registry data concerning health care utilization.

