### **Perspectives**

Persistent pain is a late effect of cancer and cancer treatment that constitutes a significant problem for the individual patient, health services and society [2, 46]. Consequently, the need exists for available evidence-based treatments for such problems to be implemented in health services [25, 47]. The project is in line with Aarhus University Hospital's desire to develop and implement evidence-based strategies for the prevention and treatment of late effects of cancer and cancer treatment. The analysis of health-economic data from our published RCT [26] showed an average savings in health services consumption (including MBCT expenses) per patient having completed therapy of approx. DKK 5,421 over an eight-month period. When this data is extrapolated to correspond to one year, savings of DKK 8,131 per participant are achieved, giving net savings for total consumption of health services of about DKK 975,780 per year for 120 patients. As such, the implementation of MBCT as a treatment program for post-treatment pain in cancer patients is expected to be cost-neutral, at minimum, while *at the same time*, expecting a clinically significant reduction in pain among those patients who accept the treatment plan.

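### Must the responder comparison be rewritten because patients with T1 pain intensity 0–1 cannot fall by 2 points?

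*Combined protocol and SAP*

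**What the plan says.** Under Statistical analysis, the main analysis is a multilevel linear model of pain over T1–T3. The section then adds: "We will also compare patients who experience statistically (Reliable Change Index) [44] and clinically significant changes", with a threshold of 2 or more NRS points, "with the remaining patients". It does not name the pain item, the direction of change or the interval. It does not say whether both criteria must be met, on what the two groups are compared, or whether anything is adjusted for. Separately, secondary analyses will "explore the possible moderating influence of demographic and clinical background variables to changes in pain".

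Three other places bear on the reading:

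- Instruments: "The primary effect measure is pain intensity", on a 0–10 scale.
- Participants: patients scoring 4 or more "on one or more of the four pain dimensions questions receive a folder describing MBCT and the treatment plan". No minimum is set for intensity itself.
- Perspectives: the authors are "expecting a clinically significant reduction in pain among those patients who accept the treatment plan".

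Screening takes place at the final oncology consultation. T1 comes later, before the first session, and no re-check of the threshold at T1 is described.

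**The concern.** Read together, these sections suggest a responder is someone whose pain intensity falls by at least 2 points. A patient admitted on burden, function or need for help may have T1 intensity 0 or 1. That patient cannot meet the rule whatever the programme does, and always lands in the comparison group. Above that floor, responder status still depends on T1 intensity, because a high score has more room to fall and regresses towards the mean.

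A background variable related to initial pain could therefore differ between responders and the rest with no link of its own to response. A reader might take it for a predictor of benefit. With no control arm, a responder proportion is also hard to interpret alone. At stake is the reading of this supplementary comparison, not the estimate of change in pain.

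**Working it through.** **1. The plan's own figure.** Participants gives about 400 eligible patients a year, 35% acceptance and 15% early drop-out: 400 × 0.35 × (1 − 0.15) = 119, which agrees with the stated 120. The plan gives no figure for the responder comparison.

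**2. The floor.** The largest possible fall equals the T1 score: 0 at T1 = 0, 1 at T1 = 1, 2 at T1 = 2. A fall of 2 needs T1 of 2 or more. Requiring the Reliable Change Index as well does not remove this. Its threshold is 1.96 × SD × √(2(1 − reliability)), which for assumed SD 2–2.5 and reliability 0.7–0.9 runs from 1.75 to 3.80 points. If change in either direction counts, the floor disappears, since a patient at 0–1 can rise by 2.

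**3. How many patients.** The documents give no baseline distribution. Simulations calibrated to the expected screen-positive share (400/3,250 = 12.3%) put 1–23% at T1 intensity 0–1, or 13–37% if T1 is a re-measurement correlated 0.8 with screening. If acceptance rises with intensity, the low end drops to 0.5%. All of these rest on assumed item correlations and SDs.

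**4. What the floor does alone.** Let q be the share at 0–1 and p the response rate among the others. The share of non-responders at 0–1 is q / (q + (1 − q)(1 − p)). With p = 0.4:

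- q = 0.05: 0.05 / (0.05 + 0.95 × 0.6) = 8%
- q = 0.30: 0.30 / (0.30 + 0.70 × 0.6) = 42%

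**5. The floor is often the smaller part.** In a second simulation (SD 2, reliability 0.6 or 0.8, true fall 0 or 1 point), responder status correlated 0.21–0.44 with T1 intensity in all patients. It still correlated 0.21–0.35 among those at 2 or more. Similarly, take a variable correlated 0.3 with T1 intensity and n = 120:

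| Pattern of fall | False differences, all patients | T1 of 2 or more only |
|---|---|---|
| 30% proportional | 13–39% | 12–31% |
| Constant 1.2 points | 5–21% | 4–6% |

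Under the proportional pattern, most of the excess is the baseline dependence that any split on a change score carries.

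**6. Does T1 adjustment cure it?** In those runs the false-difference rate fell to 4–6% after adjustment. That result is built in: the test variable was generated from *observed* T1, so conditioning on observed T1 must remove the link. Pain ratings contain error, and the same T1 error also helps decide who is a responder. At a given observed T1, responders more often had a T1 rating above their true level, so their true intensity is lower. Adjustment then pushes the difference below zero.

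With reliability 0.8, a variable correlated 0.3 with *true* intensity and no effect on true change, the group difference was +0.04 to +0.22 SD unadjusted and −0.14 to −0.19 SD adjusted. False-positive rates at n = 120, in two sets of runs of this case:

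- First set: about 8–24% adjusted against 4–19% unadjusted, with adjustment worse in most settings.
- Second set: about 6–14% adjusted. Adjustment was worse in all 12 settings with no change or a constant fall (for example 12% against 5%). It helped under a proportional fall (9–10% against 13–21%).

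Which is better depends on the unknown pattern of change.

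**7. Restricting to T1 of 2 or more.** This brings regression to the mean. With no true change, 14–23% fall and 8–13% rise by 2 points, against 11–17% each way in all patients.

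**The case for a change.** The strongest case for a change is that silence leaves item, direction and adjustment to be chosen after the data are seen, while writing them down costs a few lines. A fall in intensity is the natural reading, and under it the floor is certain. The moderator analysis does not fill the gap, since it concerns change in pain and does not name T1 intensity. With no true change, 11–17% would still count as responders, so a worsening rate alongside would be informative. Showing adjusted and unadjusted results would at least expose the sensitivity.

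Much of this stands. The rule is under-specified, the floor is real on that reading, and the comparison cannot be read as showing who benefits because of the programme. What does not stand is that the proposed repair improves the answer. Two biased contrasts, with no basis for choosing between them, are not clearly more useful than one read with caution. Naming the item and direction records what the primary measure and the expected reduction already imply. Tabulating T1 intensity by group is ordinary descriptive practice. Worsening and restricted-denominator rates would refine a responder rate that the plan does not state. The Dissemination section does not list the responder comparison either.

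**Conclusion.** No change to the plan is needed. On the natural reading, patients at T1 intensity 0–1 cannot respond and responder status is tied to T1 intensity. Harm, however, requires a fall rule, an unadjusted test, a compared variable related to T1 intensity, and a reader who takes the result as more than exploratory. The plan commits to none of these. The missing details are ones an analyst would fill sensibly. Whether to adjust for T1 is a real trade-off: about 8–24% false positives adjusted against 4–19% unadjusted, assuming reliability 0.8, a correlation of 0.3 with true intensity and n = 120. The share at 0–1 cannot be learned from the documents, and the assumed range of 0.5–37% is too wide to settle the matter. The multilevel model is unaffected. The balance would shift only if the responder comparison were used as main evidence of who benefits, which the plan does not propose.
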